the included studies presented the prescribed volume: ten replicates (11) and three series of ten repetitions (15). Some studies have also described the volume: two sets of ten repetitions (16), two to four sets of 15 to 20 seconds of contraction for isometric exercises and 15 to 20 repetitions for dynamic exercises (17). A single series of 10 replicates with a 30-second interval between the series (18,19). It is known that the literature suggests for the muscular strength gain in the elderly a training volume of two to three sets per exercise, seven to ten repetitions per set and a moderate to high intensity (8,20) and as noted most Pilates exercise programs have not followed these recommendations.

The aim of the study is to compare the effect of different volumes of Pilates exercise training on muscle strength, postural balance, flexibility, functional autonomy, depressive symptoms and lung function in the elderly community. We believe that Pilates exercises will have beneficial effects for the elderly, but our hypothesis is that the group that performs a greater volume of Pilates exercise training will have a greater improvement in the investigated outcomes than the group with the lowest volume.

Methods

Type and location of study

This is a randomized clinical trial, which will be conducted at a Pilates studio in Goiânia.

Participants

The elderly will be invited through advertisements in social networks, local media, and posters distributed in the centers of coexistence of the elderly, health centers and churches and will be selected, considering the possibility of 20 % of sample losses, the first 57 eligible participants according to the following inclusion criteria:

- Age between 60 and 85 years;
- To present cognitive aptitude according to the Mental State Mini-Exam (MMSE);
- Independent walking, without the use of auxiliary walking devices;
- Not participating in other physical intervention research;

- Not having undergone physiotherapeutic treatment and not having participated in a structured physical activity in the previous month;
- Do not present neurological diseases, history of fractures or recent surgeries and serious cardiorespiratory diseases.

Participants will be excluded:

- Failure to attend all stages of evaluation;
- They did not complete 80% of the intervention.

Outcomes and Measuring Instruments

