Initially, everyone who agrees to participate in the study will sign the informed consent form, then the data concerning the variables: cognitive ability, sociodemographic, clinical characterization, and anthropometric measurements will be collected. All participants will be evaluated for muscle strength, balance, flexibility, functional autonomy, depression and lung function before and after the intervention, including those who do not complete 80% of their presence during the intervention. For the self-report questionnaires an evaluator will be trained and for the performance questionnaires/tests two evaluators will be trained and they will be blind to the intervention. Subjects will be randomized into three groups. The randomization process will be done at random.org and concealment of the allocation will occur using opaque and sealed envelopes.

Statistical analysis plan

A sample size was calculated using the effect size identified in the comparison of the results concerning the post-intervention moment of the intervention and control groups, using data from the literature (18,25,26). The calculation indicated the need for a sample size of 15 participants per group for a power of 80% and an alpha error of 0.05 in the intergroup comparison analyzes for the variables muscle strength, balance, and flexibility.

Initially, the distribution of the data will be determined by means of the Shapiro-Wilk normality test. Subsequently, the descriptive analysis will be performed with frequency and percentage calculation for the categorical, mean and standard deviation data for continuous data with normal distribution and for median and interquartile data for continuous data with non-normal distribution.

For the comparison of the three groups for the performance of the continuous data, the ANOVA One Way test with post hoc of Bonferroni or Kruskal Wallis with Bonferroni correction (according to the normality of the data) will be used. The t-test of paired student or Wilcoxon (according to the normality of the data) will be used to compare the continuous data at the before and after moments in each group. Comparison of categorical data will be done using the chi-square test. For each primary and secondary outcome, the values observed in each group will be described, the size of the estimated effect along with its accuracy (eg, 95% confidence interval). It will be adopted 5% significance level.

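### Bonferroni after the three-group omnibus test is valid but more conservative than needed; Holm or a strictly gated closed rule, with Welch tests, would recover some pairwise power

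*Combined protocol and SAP*

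**What the plan says.** The Evaluation procedures section states: "Subjects will be randomized into three groups". These are Group A (lower volume, GA), Group B (higher volume, GB) and control (CG), so each outcome has three pairwise comparisons.

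The Statistical analysis plan, and the abstract in the same terms, compares them by "the ANOVA One Way test with post hoc of Bonferroni or Kruskal Wallis with Bonferroni correction". The level is set once: "It will be adopted 5% significance level". The words post hoc suggest that pairs are tested only after a significant omnibus result, but no such rule is written. Sidedness is not stated, nor whether the pairwise tests use a pooled SD.

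The sample size is "15 participants per group for a power of 80% and an alpha error of 0.05", for "intergroup comparison analyzes for the variables muscle strength, balance, and flexibility". It was obtained "using the effect size identified in the comparison of the results concerning the post-intervention moment of the intervention and control groups", but neither the effect size nor an SD is given. The paragraph does not mention the Bonferroni step. The Participants section recruits "considering the possibility of 20 % of sample losses, the first 57 eligible participants".

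For each outcome the plan also promises "the size of the estimated effect along with its accuracy (eg, 95% confidence interval". No adjustment across outcomes is described.

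**The concern.** Bonferroni tests each pair at 0.05/3 = 0.0167. With only three comparisons, other rules keep the chance of any false pairwise claim within an outcome at 5% and reject more often when a difference is real. With 15 to 19 people per group, power is scarce.

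There is also a gap between the sample size and the analysis. If the 80% was computed at 0.05 per comparison, the planned pairwise tests have less than 80% power. The Introduction's hypothesis is that the higher-volume group improves more than the lower-volume group, and that contrast is likely to be smaller than either group's difference from control.

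**Working it through.** **Inputs.** From the documents: three groups, 15 per group, 80% power, alpha 0.05, 20% losses, 57 recruited. Assumed: two-sided tests, normal outcomes, equal allocation and, except where stated, equal SDs.

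**1. The plan's own figures.** The total reproduces: 3 × 15 = 45, and 45/(1 − 0.20) = 56.25, rounded up to 57, or 19 per group. The 15 per group cannot be reproduced without an effect size, so it is solved backwards. For a two-sample t test with 28 df the noncentrality is d√(n/2) and the critical value is 2.048. Power reaches 80% at d = 1.06 (1.06 × √7.5 = 2.90).

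**2. Cost of the correction at that effect.** At alpha 0.05/3, the two-sample t calculation needs 21 per group for 80% power instead of 15.

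**3. Error control of the alternatives.**
- *Holm.* Order the three p-values and compare them with 0.05/3 = 0.0167, 0.05/2 = 0.025 and 0.05, stopping at the first failure. The first step is Bonferroni's and later steps are easier, so Holm rejects everything Bonferroni rejects. It needs no omnibus gate.
- *Closed rule.* If all means are equal, any false claim first needs a false omnibus result (5%). If exactly one pair is equal, one true null remains and is tested at 5%. If all differ, no false claim is possible. This argument is specific to three groups.

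Simulation (200,000 trials per scenario, n = 15, equal SDs, pooled variance) gives these family-wise error rates:

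| Rule | All means equal | One pair equal, third group far away |
|---|---|---|
| Bonferroni | 4.3% | 1.7% |
| Closed rule | 4.9% | 4.9% |

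Unadjusted tests without the gate give 12% when all means are equal, so the gate is essential to the closed rule. On the rank route, Kruskal-Wallis followed by unadjusted rank-sum tests gives 4.9% and 5.1% (100,000 trials).

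**4. Power at d = 1.06, pooled SD.**

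| Contrast | n per group | Bonferroni | Holm | Closed |
|---|---|---|---|---|
| GB v CG, with GA = CG or GA = GB | 15 | 66% | 69% | 76% |
| GB v CG, with GA halfway | 15 | 66% | 67% | 70% |
| GB v GA, with GA halfway | 15 | 16% | 21% | 28% |
| GB v CG, with GA = CG or GA = GB | 19 | 78% | 81–82% | 87% |
| GB v CG, with GA halfway | 19 | 78% | 79% | 81% |
| GB v GA, with GA halfway | 19 | 21% | 27% | 35% |

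On the rank route, when one group differs from two equal groups, the gated rule has 73% against 59–60% for Bonferroni at n = 15, and 84% against 74% at n = 19. Holm was not run on that route.

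**5. Unequal variances.** Take assumed SDs of CG 1, GA 2 and GB 2, with GA = GB and CG far away. The pooled variance is (1 + 4 + 4)/3 = 3, but the GA–GB comparison needs 4. The effective critical value falls from 2.018 (42 df) to 2.018 × √(3/4) = 1.75. By simulation, false GA v GB claims are about 9% with the pooled closed rule and 3.8% with pooled Bonferroni. Pooled Holm also reaches 5% for that last pair, so it is exposed in the same way. Holm with Welch pairwise tests gives 4.9%. With equal SDs, Welch versions cost about 2 points of power.

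**The case against.** Bonferroni is valid, standard and needs no gate. It is the only multiplicity adjustment in the plan, and it has matching simultaneous intervals, which suits a plan that promises intervals for every outcome. All of that stands, and several stronger readings should be resisted.

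- *That the plan is in error.* It is not. One valid rule would be exchanged for another.
- *That Bonferroni adds no protection.* It does. When two groups are equal and the third is far away, it holds false claims for the equal pair at about 1.7%, where the closed rule uses the full 5%. It also has more margin under unequal variances.
- *That the stated 80% power is wrong.* The documents do not say whether alpha 0.05 is per comparison or for the family. If it was already divided by three, the implied effect would be about d = 1.25, and Bonferroni at 15 per group would give about 80%.
- *That GB v GA is the contrast most harmed.* This rests on GA gaining exactly half of GB's effect, which no section supports. In that scenario GA v CG falls equally, from 28% to 16%. If GA = CG, GB v GA and GB v CG lose the same amount. The weakness of GB v GA comes mainly from sizing the trial on intervention against control, which a change of adjustment cannot repair.

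The objection does not remove the efficiency point. Holm keeps the same family-wise level, needs no gate, and gives up only the matching simultaneous intervals.

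**Conclusion.** The point holds as an efficiency improvement within each outcome. Like for like, against control at 15 per group, Holm gains about 1 to 3 points over Bonferroni and the closed rule 4 to 10; at 19 per group, about 1 to 4 and 3 to 9. These sizes rest on the back-solved d = 1.06, two-sided tests, normal data and equal SDs.

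The net gain is smaller once Welch tests are used. If the planned Bonferroni tests use a pooled SD, Welch–Holm at 15 per group has about 67 − 2 = 65% to 69 − 2 = 67% against the present 66%. Its benefit against control is then mainly protection against unequal variances. The Welch closed rule keeps a clearer net gain, about 68–74%.

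None of the rules controls error across outcomes. With six independent outcomes (the protocol names six domains) each at 5%, the chance of at least one false finding is 1 − 0.95⁶, about 26%.

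**What to change.** In the Statistical analysis plan and the abstract, replace the Bonferroni step with one of these:

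1. **Holm-adjusted pairwise tests:** Welch t tests on the ANOVA route, Wilcoxon rank-sum tests on the Kruskal-Wallis route.
2. **A strictly gated closed rule:** for each outcome, test the three pairs at 5% each only if the omnibus test is significant at 5%; otherwise claim no pairwise difference. Use Welch versions of both the omnibus and the pairwise tests on the ANOVA route, and Kruskal-Wallis followed by Wilcoxon rank-sum tests on the rank route.

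In the sample-size paragraph, give the effect size, say whether the 80% refers to an unadjusted or adjusted alpha, and restate pairwise power under the chosen rule, including GB v GA.

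The cost is wording only; no data collection changes. There are two downsides to state. The 95% intervals will not be simultaneous and should be labelled so; under the closed rule an interval may exclude zero while the gate blocks the claim. The chosen rule should also be described as controlling error within each outcome only.

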The dependent variables of the present study will be muscle strength, postural balance, flexibility, functional autonomy, depression and pulmonary function.

Muscle Strength

The muscle-dependent variable will be evaluated through the Biofeedback System for The Biofeedback System will be used for the practice of resistance exercises with elastic overload (E-lastic®), The 30-second chair stand test (30-s CST), and the palmar gripper dynamometer

- The Biofeedback System will be used for the practice of resistance exercises with elastic overload (E-lastic®). E-lastic® will measure maximal isometric voluntary contraction of the knee flexor and extensor muscles, flexors, extensors, adductors and hip abductors before and after the intervention. For the acquisition of force signals, a load cell is used to provide an electrical signal proportional to the force that deforms the equipment. The participants will perform 3 repetitions, maintaining the contraction for 5 seconds, with 60 seconds of recovery and the highest value will be recorded.
- The 30-second chair stand test (30-s CST) will be used. It consists of getting up and sitting on a chair as many times as possible within 30 seconds. A seat with backrest and without armrest (with a seat height of 45 cm) is used. Initially, participants remain seated and are instructed to look forward after command "1, 2, 3, will" they raise with their arms crossed on their chest. The evaluator will explain and demonstrate the test and the participant will do once for familiarization. You will be given a rest of 2 minutes to start the test.

- Will be measured using the Saehan® hydraulic palmar gripper dynamometer, the position recommended by the American Society of Hand Therapists (ASHT) will be adopted: sitting comfortably positioned with shoulder lightly bent, elbow bent at 90 °, forearm in neutral position and, finally, the position of the handle may vary from 0 ° to 30 ° of extension. It will be used to record the maximum and average manual grip strength of three measurements and the values will be compared with the reference values.

Postural balance

The static and dynamic body balance will be evaluated.

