- Static postural balance: will be evaluated by measuring the time each participant can maintain in three progressively more difficult positions: semi-tandem, tandem and unipodal support. In all positions the individuals must be with their hands on their waist, the total time to stay in each position is 30 seconds and it will have 3 attempts in each position and the best time will be recorded. The evaluator will demonstrate the test once.
- Dynamic postural balance: to evaluate the dynamic balance, the Timed Up and Go (TUG) test and the Step Test will be used. The TUG starts with the participant sitting in the chair, in the "go" command, he gets up from the chair, walks 3 meters at a comfortable pace, turns around, goes back to the chair and sits down. It will be demonstrated once and then it will do a repeat for familiarization. In the Alternative Step Test, the participant is asked to make eight beats of the foot, alternating between right and left, on a step in front of him with a height of 18 cm. Time will be timed and used in the analyzes. The test should be performed in 10 seconds.

Flexibility

To evaluate the flexibility of the hamstring muscles will be used the Sit and Go Test, using the Wells bench, participants will remain without footwear, sitting with knees extended, shoulders flexed, elbows extended and hands overlapped. Participants should perform trunk flexion at the front, perform a forced expiration, and move the seat ladder as far as possible, this procedure will be performed three times and immediately noted by the evaluator, with the best.

Functional Autonomy

The functional autonomy of the upper limbs will be evaluated by the dressing test and a t-shirt. Initially, the evaluator will explain the test and the volunteer will do a brief training with two replicates. The execution time is marked in seconds and the shorter the execution time, the better the result. The subject must make two attempts, where the best performance attempt will be recorded.

Depressive symptoms

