The Geriatric Depression Scale will be used for the evaluation of depressive symptoms in the elderly and screening for depression among older people. Geriatric depression scale will be presented as an interview and the questions have a yes / no format to be easy to understand. The short version consists of 15 questions, one point is given for each "yes" answer and the number of points is added to provide a single score. The score ranges from 0 to 15 and a score of zero to five is considered normal, six to ten indicates mild depression and 11 to 15 suggests severe depression.

Respiratory muscle strength

Respiratory muscle strength will be measured by assessing maximal inspiratory pressure (MIP) and maximal expiratory pressure (MEP) in cmH₂O. These measures represent the strength of the inspiratory and expiratory muscles respectively. It will be using the manometer of the brand Globalmed® MVD300, calibrated, the patient seated at 90°, a nasal clip and a nozzle connected to the equipment will be placed. In order to assess MIP, a maximum expiration up to the residual volume and, in the sequence, a maximum sustained forced inspiration will be required. And to assess PEmax inspiration will be required up to the total lung capacity and, subsequently, a forced maximum expiration up to the residual volume. Three reproducible measurements will be made, with variation less than 10% and the values found will be compared with those predicted.

Pulmonary function

Pulmonary function will also be evaluated by spirometry. The test measures forced vital capacity (FVC) in liters (L), forced expiratory volume in the first second (FEV₁) in liters (L) and the FEV₁ / FVC ratio. A One Flow® portable spirometer will be used, the individual will be seated with the head in the neutral position, inspiration will be requested up to the total lung capacity (CPT) and, thereafter, a

maximum expiration, with an explosive start, to the residual volume (lasting at least 6 seconds). A maximum of eight replications will be performed until three reproducible measures (less than 10% difference), 60 seconds of interval between measurements, will be considered the best value. It is recommended to compare the values obtained with predicted equations

Sociodemographic, Clinical, Anthropometric and Feasibility Indicators

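### The plan refers to primary and secondary outcomes but names neither, so nothing fixes which of about 22 variables must be positive to support the hypothesis

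*Combined protocol and SAP*

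**What the plan says.** The only mention of a hierarchy is in the Statistical analysis plan: "For each primary and secondary outcome, the values observed in each group will be described, the size of the estimated effect", to be given with its precision. No section says which outcomes those are. Outcomes and Measuring Instruments puts six domains on one footing: "The dependent variables of the present study will be muscle strength, postural balance, flexibility, functional autonomy, depression and pulmonary function".

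Several domains hold more than one variable. Muscle Strength includes "maximal isometric voluntary contraction of the knee flexor and extensor muscles, flexors, extensors, adductors and hip abductors before and after the intervention", a chair-stand count, and a dynamometer used to "record the maximum and average manual grip strength of three measurements". Static balance is timed in "three progressively more difficult positions: semi-tandem, tandem and unipodal support". Spirometry adds more: "The test measures forced vital capacity (FVC) in liters (L), forced expiratory volume in the first second", and the ratio of the two.

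The three groups are compared on each variable by one-way ANOVA or Kruskal-Wallis, with a Bonferroni step for the group pairs and a 5% level. The sample size rests on the "effect size identified in the comparison of the results concerning the post-intervention moment of the intervention and control groups", at 80% power "in the intergroup comparison analyzes for the variables muscle strength, balance, and flexibility".

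The Introduction gives as the hypothesis that the higher-volume group (GB) will improve more than the lower-volume group (GA). The Abstract also expects both Pilates groups to improve significantly compared with the control group (CG). Both statements speak of the outcomes collectively.

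**The concern.** The plan relies on a classification that it does not contain. The sample-size sentence comes closest to a priority, but it names three domains, not variables, and does not call them primary. GB versus GA is identifiable as the main hypothesis, but it is attached to no variable and is not the comparison behind the sample size.

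As far as this document goes, the variable that carries a GB-over-GA claim could therefore be settled after the results are known. The chance of a false claim would then depend on whatever rule is applied at that stage. Bonferroni does not close the gap, because it works within each variable and not across variables.

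**Working it through.** **1. The plan's own figure.** 15 / (1 − 0.20) = 18.75, rounded up to 19 per group; 19 × 3 = 57, as stated under Participants. The 15 itself cannot be reproduced, because no effect size is given. If it came from a two-sided two-sample t-test at 5% (an assumption), 80% power implies a standardised difference d of 1.06: noncentrality 1.06 × √(15/2) = 2.90 on 28 degrees of freedom.

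**2. Count of variables.**

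| Domain | Variables | Number |
|---|---|---|
| Strength | 6 isometric, chair stand, grip maximum and average | 9 |
| Balance | 3 static positions, TUG, Step Test | 5 |
| Flexibility | sit-and-reach | 1 |
| Functional autonomy | dressing test | 1 |
| Depressive symptoms | GDS | 1 |
| Respiratory | MIP, MEP, FVC, FEV1, FEV1/FVC | 5 |
| Total | | 22 |

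The total is 21 if grip is tested once; two grip tests are an inference. It would be higher if limbs were analysed by side, which is not stated. The sized domains hold 9 + 5 + 1 = 15.

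**3. Error for one named variable.** With no true effect, each pair is tested at 0.05/3 = 0.0167 two-sided, so about 0.0083 in the direction GB over GA. Requiring a significant ANOVA first brings this to 0.0081, or 0.8%.

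**4. Error if any one variable may carry the claim.** Simulation inputs: no true effect, 15 per group, normal data, omnibus F at 5%, then pairwise tests at 0.05/3 with pooled variance (42 degrees of freedom). The documents give no correlations, so a common value is assumed and varied.

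| False claim | r = 0.9 | r = 0.7 | r = 0.5 |
|---|---|---|---|
| GB over GA, any of 22 | 3% | 7% | 10% |
| GB over GA, any of the 15 in sized domains | 3% | 5% | 8% |
| GA and GB both over CG, on the same variable | 0.6% | 1.4% | 1.6–1.9% |
| GA and GB both over CG, different variables allowed | 0.7% | 1.8% | 2.4–2.8% |
| Either Pilates group over CG, any of 22 | 6% | 11–12% | 16–17% |

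Ranges show the spread between separate simulation runs. Zero correlation gives an upper reference for GB over GA: 1 − (1 − 0.0081)^22 = 0.16, or 0.17 with 0.0083; for 15 variables, 1 − (1 − 0.0081)^15 = 0.11 to 0.12. At zero correlation both Pilates groups beat control in at most about 4.5% of trials.

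With unequal correlations (within/between domains 0.9/0.5, 0.7/0.3, 0.5/0.2), GB over GA is 7%, 10% and 12%.

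**5. A stricter rule.** If at least 11 of the 22 variables must be positive, false GB over GA is at most 0.6% for correlations from 0 to 0.9.

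**6. Power under a named primary.** At d = 1.06 and 15 per group, one contrast at 5% has 80% power. At the first Holm step for three variables (0.05/3) it has 64%.

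The before/after tests within each group are not part of these figures.

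**The case against.** The strongest reply is that the plan is more disciplined than the missing label suggests. It states GB versus GA as its hypothesis, corrects the group pairs, and promises effect sizes with confidence intervals. The Abstract asks that both Pilates groups beat control, a demanding conjunction whose false-positive rate stays below 5% even when any variable may count. Improvement in the outcomes collectively reads more naturally as a broad pattern than as a single hit, and a rule of that kind inflates nothing. All of this stands, and it limits the point to an open error rate.

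It does not remove the gap. The plan states neither the lenient nor the strict rule, and estimates with intervals do not say which outcome carries the claim. Treating the sized domains as implicitly primary still leaves 15 variables.

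Three stronger readings are tempting and are not supported:

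- **A chance of about 68% of a false finding**, from 1 − 0.95^22. This treats the variables as independent and counts omnibus tests, which by themselves support no directional claim.
- **A false-benefit rate of 8%, 16% or 23%** (39% at zero correlation). This counts any of three contrasts on any variable, a doubly permissive rule that the documents do not adopt.
- **No main contrast exists at all.** The Introduction does state one; it lacks a variable and a matching sample size.

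A designation may also exist in a registry record. None was available, so the point is limited to this document.

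**Conclusion.** The omission is real and should be corrected. The plan uses a primary/secondary distinction that it never fills in, and nothing controls or fixes the error rate across about 22 variables. Under the most permissive rule, a false GB-over-GA claim rises from 0.8% to about 3–10% for correlations of 0.9 to 0.5, with 16–17% as the upper reference. A claim that either Pilates group beats control reaches about 6% to 17%. The claim that both do stays at about 0.6–3%.

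These figures assume normal data, 15 per group, no true effect and correlations that are not in the documents. A reader should not infer that the trial's error rate is high: under a stricter rule it is not. What the document shows is that the rate depends on a choice not yet made.

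**What to change.** Before outcome data are examined, amend the Statistical analysis plan as follows.

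- Name one primary variable from strength, balance or flexibility, and one primary between-group contrast tested two-sided at 5%. The contrast is the sponsor's choice: a Pilates group versus control matches the basis of the sample size, while GB versus GA matches the stated hypothesis.
- If the three sized domains are to share primary status, name one variable for each, use the same contrast for all three, and apply Holm across them.
- Declare every other variable and contrast secondary, reported as estimates with 95% confidence intervals under the planned ANOVA and Bonferroni procedure.
- Restate power if GB versus GA is primary, because the 80% came from intervention-versus-control effects and no GB-versus-GA effect is given. Restate it also if Holm is used: about 64% first-step power at 15 per group, if the 15 came from a two-sided t-test with d = 1.06.

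The cost is SAP wording and fewer results that can be called confirmatory. A single Pilates-versus-control primary needs no extra participants on the plan's own sizing. Under the same assumption, restoring 80% at the first Holm step would take 21 per group: 21/0.8 = 26.25, rounded up to 27, and 27 × 3 = 81 in total.
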